Grade 4	Permanently discontinue study drug/study regimen	 should typically be administered in a monitored setting under supervision of a consulting neurologist. Patients unable to tolerate steroids may be candidates for treatment with plasmapheresis or IVIG. If Myasthenia Gravis-like neurotoxicity present, consider starting acetylcholine esterase (AChE) inhibitor therapy in addition to steroids. Such therapy, if successful, can also serve to reinforce the diagnosis. GUILLAIN-BARRE: Important to consider here that the use of steroids as the primary treatment of Guillain-Barre is not typically considered effective. Patients requiring treatment should be started with IVIG and followed by plasmapheresis if not responsive to IVIG

	Table 2- Infusion-Related Reactions			
Severity Grade	Dose Modifications	Toxicity Management		
Any Grade		 Management per institutional standard at the discretion of investigator Monitor patients for signs and symptoms of infusion-related reactions (e.g., fever and/or shaking chills, flushing and/or itching, alterations in heart rate and blood pressure, dyspnea or chest discomfort, skin rashes etc.) and anaphylaxis (e.g., generalized urticaria, angioedema, wheezing, hypotension, tachycardia, etc.) 		
Grade 1	The infusion rate of study drug/study regimen may be decreased by 50% or temporarily interrupted until resolution of the event	 For Grade 1 or Grade 2: Acetaminophen and/or antihistamines may be administered per institutional standard at the discretion of the investigator Consider premedication per institutional standard prior to subsequent doses 		
Grade 2	The infusion rate of study drug/study regimen may be decreased 50% or temporarily interrupted until resolution of the event			
	Subsequent infusions may be given at 50% of the initial infusion rate			
Grade 3/4		For Grade 3 or 4:		
	Permanently discontinue study drug/study regimen	Manage severe infusion-related reactions per institutional standards (e.g., IM epinephrine, followed by IV diphenhydramine and ranitidine, and IV glucocorticoid)		

	Table 3- Non-immune Mediated Reactions (Note: As applicable, for early phase studies, the following sentence may be added: "Any event greater than or equal to Grade 2, please discuss with Study Physician"			
(Note: As applical				
CTC Grade/Severity	Dose Modification	Toxicity Management		
Any Grade	Note: dose modifications are not required for adverse events not deemed to be related to study treatment (i.e. events due to underlying disease) or for laboratory abnormalities not deemed to be clinically significant.	Treat accordingly as per institutional standard		
1	No dose adjustment	Treat accordingly as per institutional standard		
2	Hold study drug/study regimen until resolution to \leq Grade 1 or baseline	Treat accordingly as per institutional standard		
3	Hold study drug/study regimen until resolution to \leq Grade 1 or baseline For AEs that downgrade to \leq Grade 2 within 7 days or resolve to \leq Grade 1 or baseline within 14 days, resume study drug/study regimen administration at next scheduled dose. Otherwise, discontinue study drug/study regimen	Treat accordingly as per institutional standard		
4	Discontinue Study drug/study regimen (Note for Grade 4 labs, decision to discontinue would be based on accompanying clinical signs/symptoms and as per Investigator's clinical judgment and in consultation with the sponsor)	Treat accordingly as per institutional standard		

Abbreviations:

AChE = acetylcholine esterase; ADA = American Dietetic Association; AE = adverse event; ALP = alkaline phosphatase; ALT = alanine aminotransferase; AST = aspartate aminotransferase; CT = computed tomography; GI = gastrointestinal; IDS=Infectious Disease Service; ILD = interstitial lung disease; IM = intramuscular; irAE = immune-related adverse event; IV = intravenous; NCI CTCAE = National Cancer Institute Common Terminology Criteria for Adverse Events; PO = by mouth; TNF = tumor necrosis factor; TSH = thyroid stimulating hormone; ULN = upper limit of normal.

¹ ASCO Educational Book 2015 "Managing Immune Checkpoint Blocking Antibody Side Effects" by Michael Postow MD
 ¹ NCI CTCAE version 4.03
 ¹ ASCO Educational Book 2015 "Managing Immune Checkpoint Blocking Antibody Side Effects" by Michael Postow MD

¹ FDA Liver Guidance Document 2009 Guidance for Industry: Drug Induced Liver Injury – Premarketing Clinical Evaluation

Appendix 2: Schedule of study procedures: follow-up for subjects who have completed treatment or have discontinued treatment due to toxicity

Evaluation ^a			
	Month 1	Month 2	Month 3
Physical examination	Х	X	Х
Vital signs (temperature, respiratory rate, blood pressure, pulse)	Х	X	X
Weight	Х	X	X
Urine hCG or serum βhCG	Х		
AE/SAE assessment	Х	X	X
Concomitant medications	Х	X	X
ECOG performance status	Х	X	X
Subsequent anti-cancer therapy			X
Hematology	Х	X	X
Serum chemistry	X	X	X
Thyroid function tests (TSH, and fT3 and fT4) ^b	X		
sPD-L1 concentration (to assess target engagement), if applicable		X	

^a A follow up visit for evaluation is preferred and will be scheduled monthly for 3 mo after the last administration of Durvalumab whenever possible. Alternatively, available data will be collected from medical records and phone evaluation will be attempted as well.

^b Free T3 and free T4 will only be measured if TSH is abnormal. They should also be measured if there is clinical suspicion of an adverse event related to the endocrine system.

Appendix 3 – Subject Eligibility Checklist

IRB Protocol No.	CCCWFU Protocol No.	
Study Title:		
Principal Investigator: [name]		

Inclusion Criteria (as outlined in study protocol)	Criteria is met	Criteria is NOT met	Source Used to Confirm * (Please document dates and lab results)
Histologically or cytologically confirmed HNSCC of the oral cavity (OC; more than 90% patients have HPV negative cancer) or oropharynx (about 60-80% of patient have HPV positive cancer).			
Presence of radiologically or clinically documented disease. All radiology studies must be performed within 28 days prior to registration.			
Any stage, considered candidates for surgery and planned for surgery either by robotic or by standard surgical technique.			
Documentation of HPV tested by PCR (resulted or pending)			
Willing to provide consent for an additional tissue biopsy for research purposes, to allow a part of their surgical tumor tissue to be utilized for research, (in case tumor tissue has not already been saved in the Tumor Tissue Bank), and to donate samples of blood and saliva collected before and after treatment			
All patients must have provided informed consent for correlative studies			
ECOG performance status of 0, 1, or 2			
Patients must have no prior exposure to immune-mediated therapy, including anti-CTLA-4, anti-PD-1, anti-PD-L1, or anti-programmed cell death ligand 2 antibodies, excluding therapeutic anticancer vaccines.			
At least 1 lesion, not previously irradiated, that can be accurately measured at baseline as ≥ 10 mm in the longest diameter (except lymph nodes, which must have a short axis ≥ 15 mm) with CT or MRI or clinical measurement and that is suitable for accurate repeated measurements as per RECIST 1.1 guidelines.			
Previous surgery is permitted provided that a minimum of 28 days (4 weeks) have elapsed between any major surgery and date of registration, and that wound healing has occurred			
Absolute neutrophil count (ANC) $\geq 1.5 \times 10^{9}/L$			
Platelet count $\geq 100 \times 10^9/L$			
Hemoglobin $\ge 9.0 \text{ g/dL}$			

Serum bilirubin $\leq 1.5 \text{ x ULN}$ (institutional upper limit of normal) Total Bilirubin is less than or equal to ULN, except the case in which the elevated total bilirubin is not a sign of liver disease, such as the Gilbert Syndrome, in which case a Total Bilirubin less than or equal to 2X ULN is acceptable.		
AST and ALT \leq 2.5 x ULN		
Serum creatinine CL>40 mL/min by the Cockcroft-Gault formula (Cockcroft and Gault 1976) or by 24-hour urine collection for determination of creatinine clearance:		
Males:Creatinine CL= $\frac{\text{Weight (kg) x (140 - Age)}}{72 \text{ x serum creatinine (mg/dL)}}$ (mL/min)72 x serum creatinine (mg/dL)Females:		
Creatinine CL = $\frac{\text{Weight (kg) x (140 - Age)}}{\text{(mL/min)}}$ x 0.85 72 x serum creatinine (mg/dL)		
Female subjects must either be of non-reproductive potential (ie, post-menopausal by history: ≥60 years old and no menses for ≥1 year without an alternative medical cause; OR history of hysterectomy, OR history of bilateral tubal ligation, OR history of bilateral oophorectomy) or must have a negative serum pregnancy test upon study entry		
In accordance with NCIC CTG policy, protocol treatment is to begin within 2 working days of patient registration		
Written informed consent and any locally-required authorization (e.g., HIPAA in the USA, EU Data Privacy Directive in the EU) obtained from the subject prior to performing any protocol-related procedures, including screening evaluations		
Age \geq 18 years at time of study entry		
Subject is willing and able to comply with the protocol for the duration of the study including undergoing treatment and scheduled visits and examinations including follow up		

Exclusion Criteria (as outlined in study protocol)	Criteria NOT present	Criteria is present	Source Used to Confirm * (Please document dates and lab results)
Involvement in the planning and/or conduct of the study (applies to both AstraZeneca staff and/or staff at the study site). Previous enrolment in the present study			
Participation in another clinical study with an investigational product during the last 6 mo			
Any previous treatment with a PD1 or PD-L1 inhibitor, including Durvalumab			
Receipt of any anti-cancer therapy (chemotherapy, immunotherapy, endocrine therapy, targeted therapy, biologic therapy, tumor embolization, monoclonal antibodies, other investigational agent) within the last 6 months before the first dose of Durvalumab			
Mean QT interval corrected for heart rate (QTc) ≥470 ms calculated from 3 electrocardiograms (ECGs) using Frediricia's Correction			
Current or prior use of immunosuppressive medication within 28 days before the first dose of durvalumab, with the exceptions of intranasal and inhaled corticosteroids or systemic corticosteroids at physiological doses, which are not to exceed 10 mg/day of prednisone, or an equivalent corticosteroid			
Any unresolved toxicity (>CTCAE grade ≥ 2) from previous anti-cancer therapy. Subjects with irreversible toxicity that is not reasonably expected to be exacerbated by the investigational product may be included (e.g., hearing loss, peripherally neuropathy)			
Any prior Grade \geq 3 immune-related adverse event (irAE) while receiving any previous immunotherapy agent, or any unresolved irAE >Grade 1			
Active or prior documented autoimmune disease within the past 2 years NOTE: Subjects with vitiligo, Grave's disease, or psoriasis not requiring systemic treatment (within the past 2 years) are not excluded			
Active or prior documented inflammatory bowel disease (e.g., Crohn's disease, ulcerative colitis)			
History of primary immunodeficiency			
History of allogeneic organ transplant			
History of hypersensitivity to Durvalumab or any excipient			
History of pneumonitis or interstitial lung disease			
Subjects with uncontrolled seizures			
Uncontrolled intercurrent illness including, but not limited to, ongoing or active infection, symptomatic congestive heart failure, uncontrolled hypertension, unstable angina pectoris, cardiac arrhythmia, active peptic ulcer disease or gastritis, active bleeding diatheses including any subject known to have evidence of acute or chronic hepatitis B, hepatitis C or human immunodeficiency virus (HIV), or psychiatric illness/social situations that would limit compliance with study requirements or compromise the ability of the subject to give written informed consent			
Known history of previous clinical diagnosis of tuberculosis			
Receipt of live attenuated vaccination within 30 days prior to study entry or within 30 days			
---	--	--	
of receiving Durvalumab			
Female subjects who are pregnant, breast-feeding or male or female patients of			
reproductive potential who are not employing an effective method of birth control			
Patients with body weight <30 kg			
Any condition that, in the opinion of the investigator, would interfere with evaluation of study treatment or interpretation of patient safety or study results			
This subject is 🔄 eligible / 🗌 ineligible for participation in this study.			
WISER Assigned PID:			

Appendix 4 – Protocol Registration Form

DEMOGRAPHICS									
Patient: Last Name:	First Name:								
MRN:	OOB (mm/dd/yy) / / /								
ZIPCODE:									
SEX: □ Male □ Female	Ethnicity (choose one): 🛛 Hispanic								
	□Non-Hispanic								
Race (choose all that apply):	□BLACK □ ASIAN								
	SLANDER								
Height:inches	Weight:lbs.(actual)								
Surface Area:m²									
Primary Diagnosis:									
Date of Diagnosis: / //									
Performance Status:] Karnofsky								
PROTOCOL INFORMATION									
	///								
MD Name (last) :									
Date protocol treatment started:	///								
Informed written consent: [(consent must be signed prior to registration)	⊐YES □NO								
• ,	///								
PID # (to be assigned by WISER):									
Protocol Registrar can be contact by calling [name] between 8:30 AM and 4:00 PM, Monday – Friday.								

Completed Eligibility Checklist and Protocol Registration Form must be hand delivered, faxed or e-mailed to the registrar at [name] or [contact].

1. Are you:

Hispanic or Latino/a

Appendix 5 – Race & Ethnicity Verification Form

Thank you so much for helping us to verify your race and ethnicity to ensure the quality of our information. As a brief reminder, the information you provide today will be kept confidential.

	Not Hispanic or Latino/a	
2.	 What is your race? One or more categorie White or Caucasian Black or African American American Indian or Alaskan Native Asian Native Hawaiian or Other Pacific Islan Other, Please Specify:	der
Internal u	ise only:	
Name: _	MRN#:	
	self-reported race and ethnicity of the particles	cipant verified at the time of consent?
	screpancy found?	he EMR:
	Ethnicity:	Race:
Additional	comments:	

Appendix 6 – Mandatory DSMC SAE Reporting Guidelines

Data and Safety Monitoring	Date: 02/11/2021
Committee (DSMC) Serious Adverse	
Event (SAE) Notification SOP	

Mandatory DSMC SAE Reporting Requirements in WISER

This document describes reporting requirements of adverse events from WFBCCC Investigator Initiated interventional trials to the Data and Safety Monitoring Committee (DSMC). A trial is considered a WFBCCC Investigator Initiated interventional trial if the following criteria are met:

- 1) The Principal Investigator (PI) of the trial is a member of a department at the Wake Forest University Baptist Medical Center.
- 2) WFBCCC is considered as the primary contributor to the design, implementation and/or monitoring of the trial.
- The trial is designated as "Interventional" using the Clinical Research Categories definitions provided by the NCI in the Data Table 4 documentation. (https://cancercenters.cancer.gov/GrantsFunding/DataGuide#dt4)

There are two distinct types of WFBCCC Investigator Initiated interventional trials based on where patient enrollment occurs. These include:

- Local WFBCCC Investigator Initiated interventional trials defined as trials where all patients are enrolled from one of the WFBCCC sites. These include the main outpatient Cancer Center clinics (located in Winston-Salem) as well as WFBCCC affiliate sites located in Bermuda Run (Davie Medical Center), Clemmons, Lexington, High Point, or Wilkesboro.
- 2) Multi-Center WFBCCC Investigator Initiated interventional trials defined as trials where patients are enrolled from other sites in addition to WFBCCC sites. There are three types of trials that are included in this category:
 - a. Trials sponsored by the NCI Community Oncology Research Program (NCORP) that are conducted at multiple sites where the PI is a member of a department at the Wake Forest University Baptist Medical Center.
 - b. Trials sponsored by Industry that are conducted at multiple sites and the PI is a member of a department at the Wake Forest University Baptist Medical Center.
 - c. Trials sponsored by WFBCCC that are conducted at multiple sites and the PI is a member of a department at the Wake Forest University Baptist Medical Center.

All Adverse Events (AEs) and Serious Adverse Events (SAEs) that occur on any patients enrolled on WFBCCC Investigator Initiated Interventional trials must be entered into the WISER system. The only exception to this requirement is for patients enrolled on NCORP trials at non- WFBCCC sites. AEs and SAEs for NCORP patients enrolled at WFBCCC sites must be entered into the WISER system. Once these

AEs and SAEs are entered in WISER, certain actions must be taken regarding the reporting of specific Adverse Events to the DSMC.

All Adverse Events that occur during protocol intervention (defined below) and are coded as either 1) **unexpected grade 4,** 2) **unplanned inpatient hospitalization > 24 hours (regardless of grade)**, or **grade 5 (death)** must be reported to the DSMC using the using the SAE console in WISER.

A research nurse or clinical research coordinator when made aware that an adverse event meets one of the above criteria has occurred on a WFBCCC Investigator Initiated interventional trial, is responsible for informing a clinical member of the DSMC by phone (or in-person) about the adverse event. The nurse/coordinator should contact the treating physician prior to calling the DSMC clinical member to obtain all details of the SAE, as well as all associated toxicities to be recorded along with the SAE. In addition, this nurse or coordinator is responsible for entering the adverse event information into the SAE console in WISER. Once the adverse event has been entered into the SAE console an email informing the entire DSMC will be generated.

THESE REPORTING REQUIREMENTS APPLY TO any staff member on the study team for a WFBCCC Institutional Interventional trial. Ultimately, the protocol PI has the primary responsibility for AE identification, documentation, grading and assignment of attribution to the investigational agent/intervention. However, when an AE event as described above is observed, it is the responsibility of the person who observed the event to be sure that it is reported to the DSMC.

What is considered during protocol intervention?

During protocol intervention is considered to be the time period while a patient is on study treatment or during the time period within 30 days of last study treatment (even if patient begins a new (non-study) treatment during the 30 days). This window of 30 days should be the standard window to be used in all protocols unless a specific scientific rationale is presented to suggest that a shorter window can be used to identify events. If it is a trial sponsored by Industry and the sponsor requires a longer window for monitoring of SAEs, then the longer window of time specified by the sponsor should be followed.

What is considered as an Unexpected Grade 4 event?

Any grade 4 event that was not specifically listed as an expected adverse event in the protocol should be considered as unexpected. A grade 4 adverse event can be considered to be unexpected if it is an event that would not be expected based on the treatment being received or if it is unexpected based on the health of the patient. In either case, if there is any uncertainty about whether a grade 4 adverse event is expected or unexpected it should be reported to DSMC.

DSMC notification responsibilities of the person (e.g., nurse) handling the reporting/documenting of the SAE in WISER:

1. Make a phone call (or speak in person) to the appropriate clinical member of the DSMC according to the schedule as listed below (page if necessary).

Clinical Study Protocol Drug Substance Durvalumab (MEDI4736) Study Number **ESR-15-11576** Edition Number 5 Date 05/23/16 WFU Date 03/31/17

- 2. Enter a new SAE into the SAE module that is located in the Subject>> CRA Console inWISER WITHIN 24 HOURS of first knowledge of the event. Information can be entered and saved, but the DSMC members will not be notified until a date is entered into the DSMC Notification Date Field. This will ensure that all persons that need to be made aware of the event (i.e., PI, study team members and DSMC members) will be notified; remember to file a copy of the confirmation.
- 3. Document that the appropriate person(s) on the DSMC has been contacted. Indicate the name of the DSMC clinician that was contacted and the date and time contacted in the Event Narrative field in the SAE console of the particular subject.
- 4. Document whether or not the protocol should be suspended based on the discussion with the DSMC clinician. This is the major function of the email notification. Enter whether the protocol should be suspended in the Event Narrative Field.
- 5. Follow up/update the clinical member(s) of DSMC regarding any new developments or information obtained during the course of the SAE investigation and reporting process.

Elements needed to complete the SAE form in the Subject Console in WISER (see Screen Shot 3):

- 1. Event Date
- 2. Reported Date
- 3. Reported by
- 4. If Grade 5, enter Death Date
- 5. If Grade 5, enter Death occurred: within 30 days
- 6. Event Narrative: Brief description (include brief clinical history relevant to this event, including therapies believed related to event). Begin narrative with the DSMC clinician who was notified and Date/Time notified. In addition, state attribution by DSMC clinician as either "Unrelated", "Unlikely", "Possibly", "Probably", or "Definitely". Always include the following here:
 - i. DSMC clinician name, date/time contacted and comments
 - ii. Date of last dose before the event
 - iii. Is suspension of the protocol needed? Y/N
- 7. Treating Physician comments
- 8. PI comments, if available
- 9. Protocol Attribution after discussion with DSMC clinician
- 10. Outcome (Fatal/Died, Intervention for AE Continues, Migrated AE, NotRecovered/Not Resolved, Recovered/Resolved with Sequelae, Recovered/Resolved without Sequelae, Recovering and Resolving)
- 11. Consent form Change Required? Y/N
- 12. SAE Classification *This is required in order for the email notification to be sent*
- 13. Adverse Event Details Enter all details for each AE associated with the SAE.
 - a. Course start date
 - b. Category
 - c. AE Detail

Clinical Study Protocol Drug Substance Durvalumab (MEDI4736) Study Number **ESR-15-11576** Edition Number 5 Date 05/23/16 WFU Date 03/31/17

- d. Comments
- e. Grade/Severity
- f. Unexpected Y/N
- g. DLT Y/N
- h. Attributions
- i. Action
- j. Therapy
- k. Click ADD to attach the AE Detail to the SAE.
- 14. Enter Date Notified DSMC -- *This is required for the email notification to be sent*

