10.3.1 Study recording period and follow-up for adverse events and serious adverse events

Adverse events and serious adverse events will be recorded from time of signature of informed consent, throughout the treatment period and including the follow-up period (90 days after the last dose of durvalumab. This applies also in the situation when Durvaluamb was discontinued and patient was removed from the clinical study.

During the course of the study all AEs and SAEs should be proactively followed up for each subject. Every effort should be made to obtain a resolution for all events, even if the events continue after discontinuation/study completion.

The investigator is responsible for following all SAEs until resolution, until the subject returns to baseline status, or until the condition has stabilized with the expectation that it will remain chronic, even if this extends beyond study participation.

Follow-up of unresolved adverse events

Any AEs that are unresolved at the subject's last visit in the study are followed up by the investigator for as long as medically indicated. After 90 days, only subjects with ongoing investigational product-related SAEs will continue to be followed for safety. AEs are documented in Appendix 7.

AstraZeneca/MedImmune retains the right to request additional information for any subject with ongoing AE(s)/SAE(s) at the end of the study, if judged necessary.

Post study events

After the subject has been permanently withdrawn from the study, there is no obligation for the investigator to actively report information on new AE or SAEs occurring in former study subjects after the 90-day safety follow-up period for patients treated with durvalumab. However, if an investigator learns of any SAEs, including death, at any time after the subject has been permanently withdrawn from study, and he/she considers there is a reasonable possibility that the event is related to study treatment, the investigator should notify AstraZeneca/MedImmune Drug Safety.

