10.3.2 Reporting of serious adverse events

DSMC SAE Reporting Requirements

The Data Safety Monitoring Committee (DSMC) is responsible for reviewing SAEs for CCCWFU Institutional studies as outlined in Appendix 6. DSMC currently requires that all unexpected 4 and all grade 5 SAEs on these trials be reported to them for review. All CCCWFU Clinical Research Management (CRM) staff members assisting a Principal Investigator in investigating, documenting and reporting an SAE qualifying for DSMC reporting are responsible for informing a clinical member of the DSMC as well as the entire committee via the email notification procedure of the occurrence of an SAE.

WFUHS IRB AE Reporting Requirements

Any unanticipated problems involving risks to subjects or others and adverse events shall be promptly reported to the IRB, according to institutional policy. Reporting to the IRB is required regardless of the funding source,

study sponsor, or whether the event involves an investigational or marketed drug, biologic or device. Reportable events are not limited to physical injury, but include psychological, economic and social harm. Reportable events may arise as a result of drugs, biological agents, devices, procedures or other interventions, or as a result of questionnaires, surveys, observations or other interactions with research subjects.

All members of the research team are responsible for the appropriate reporting to the IRB and other applicable parties of unanticipated problems involving risk to subjects or others. The Principal Investigator, however, is ultimately responsible for ensuring the prompt reporting of unanticipated problems involving risk to subjects or others to the IRB. The Principal Investigator is also responsible for ensuring that all reported unanticipated risks to subjects and others which they receive are reviewed to determine whether the report represents a change in the risks and/or benefits to study participants, and whether any changes in the informed consent, protocol or other study-related documents are required.

Any unanticipated problems involving risks to subjects or others occurring at a site where the study has been approved by the WFUHS IRB (internal events) must be reported to the WFUHS IRB within 7 calendar days of the investigator or other members of the study team becoming aware of the event.

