It is the responsibility of the DSMC clinician to review all reported events, evaluate the events as they are reported; and communicate a response to the Investigator, event reporter and the members of DSMC. The review will include but not be limited to the information reported; there may be times when additional information is needed in order for an assessment to be made and further communication directly with the investigator may be warranted. DSMC reserves the right to disagree with the Investigator's assessment. If DSMC does not agree with the Investigator, DSMC reserves the right to suspend the trial pending further investigation. If there is any immediate danger or harm that could be present for a future patient based on the information provided in the DSMC report then an immediate suspension of enrollment shouldbe considered.

AMENDMENTS TO PREVIOUS REPORTS

If all pertinent information is unavailable with the initial submission, once the additional information is available **do not submit a new report**. Rather, go to the original email that was sent to the DSMC and using that email "reply to all". Entitle this new email "**Amendment** for (list date of event and patient ID)" this will avoid duplications of the same event. List the additional information being reported. This information needs to be entered into WISER as well. To do this, go to the Subject console and click SAEs on the left column. Click on the appropriate SAE number that needs updating. Then click Update. This will allow additional information to be added.

Acronyms

AE – Adverse Event

DSMC-Data and Safety Monitoring Committee

SAE-Serious Adverse Event

WFBCCC - Wake Forest Baptist Comprehensive Cancer Center

NCI-National Cancer Institute

WISER – Wake Integrated Solution for Enterprise Research

Screen Shots:

The following screen shots come from the SAE Console within the Subject Console in WISER.

Screen Shot 1:

* Subject Console																?
Protocol No.: CCCWFU88215								Protocol Status	s: OPEN 1	TO ACCRU	AL				Subject Status: C	N TREATMENT
MRN:								Subject	Name:						Sequenc	e No.: Presson
Switch Subject	Subject Demogr	Subject Demographics											History			
Type here to search		MR24														
Summary		Last Name Birth Date	_			First Name		Ein	ired Date		Middle	Name			Suffix Last Date Known A	62
Demographica		Gender								Non-Hispa	nic				Lan Date Nation A	ne
Consent		Race	White													
Consent		Subject Comments														

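### By default, mandatory DSMC review of a durvalumab-related death or unexpected grade 4 event stops 30 days after the last dose, although the protocol follows safety to 90 days

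*Combined protocol and SAP*

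**What the plan says.** Section 10.3.2 states that the DSMC "is responsible for reviewing SAEs for CCCWFU Institutional studies as outlined in Appendix 6". It names unexpected grade 4 and all grade 5 serious events as reportable, but gives no time window of its own.

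Appendix 6 supplies the window. The duty covers "All Adverse Events that occur during protocol intervention (defined below" that are unexpected grade 4, an unplanned inpatient stay of more than 24 hours, or grade 5. Protocol intervention means active treatment, plus whatever falls "during the time period within 30 days of last study treatment (even if patient begins a new (non-study) treatment during the 30 days". The appendix adds: "This window of 30 days should be the standard window to be used in all protocols". It foresees a scientific rationale only for a shorter window. One clause allows a longer one: "If it is a trial sponsored by Industry and the sponsor requires a longer window for monitoring of SAEs", the sponsor's window is to be followed.

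The body of the protocol uses a different period. Section 10.3.1 records adverse and serious adverse events "from time of signature of informed consent, throughout the treatment period and including the follow-up period (90 days after the last dose of durvalumab". Section 10.3.3 covers deaths through the same 90 days. Appendix 2 plans visits at months 1, 2 and 3 after the last dose, whenever possible.

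**The concern.** The DSMC is the only committee to which the documents give a stated right to suspend the trial. If it disagrees with the investigator's assessment, "DSMC reserves the right to suspend the trial pending further investigation". Each notification also obliges staff to do the following: "Document whether or not the protocol should be suspended based on the discussion with the DSMC clinician". An event outside the mandatory window need not trigger that step.

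The patients have potentially curable disease and are about to have surgery or have just had it. Recruitment is planned over about 18 months, with up to 6 more for replacements, so review of one late event could still protect later patients. Section 3.3 does not fill this role. It stops the study only when more than 3 patients are affected, so a single event cannot trigger it.

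**Working it through.** The plan states no figure to reproduce. The check compares the safety windows and then does day arithmetic, with the last dose as day 0.

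| Purpose | Where | Ends after last dose |
|---|---|---|
| Mandatory DSMC reporting (default) | Appendix 6 | day 30 |
| Recording of adverse and serious adverse events | Section 10.3.1 | day 90 |
| Reporting of deaths | Section 10.3.3 | day 90 |
| Reporting of serious events to the company | Section 10.3.2 | day 90, or start of alternative anticancer therapy |
| Planned safety visits | Appendix 2 | month 3 |

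**Does the longer-window clause apply?** It needs an industry-sponsored trial whose sponsor requires a longer period.
- Against: Section 10.3.2 labels this an investigator-sponsored study. Section 10.3.5 lists the sponsor and AstraZeneca as separate recipients. Appendix 6 names industry-sponsored trials only as a multi-center type, and the synopsis gives one center.
- For: the 90-day period for serious events sits under the sponsor-requirements part of Section 10.3.2, and Section 14.1 speaks of AstraZeneca clinical studies.

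Nothing in the text I had settles it, so the 30-day default is the safer reading of what staff would apply.

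**Length of the gap**
- 90 − 30 = 60 days (days 31 to 90); 60/90 = 67% of the follow-up days.
- Surgery falls 3 to 17 days after the last dose (Section 3.1). The default DSMC window closes 30 − 17 = 13 to 30 − 3 = 27 days after surgery.
- The protocol's own window closes 90 − 17 = 73 to 90 − 3 = 87 days after surgery.
- The visits at months 2 and 3 fall after day 30: 2 of the 3 planned visits.

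**With a 90-day window** for the events named in the fix, the gap is 90 − 90 = 0 days, and DSMC coverage after surgery rises from 13–27 days to 73–87 days.

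**The case against.** The strongest reply is that late events are already well covered.
- Section 10.3 says a serious event requires immediate notification to AstraZeneca's safety group.
- Section 10.3.3 requires deaths not clearly due to progression to be reported as serious events within 24 hours.
- Section 10.3.2 sends events to the FDA where regulations require, and unanticipated problems to the IRB within 7 calendar days.
- Section 10.1.3 calls for rapid communication of events of special interest, and Section 10.3.6 for 24-hour reporting of hepatic function abnormality.
- The Section 3.3 count has no day limit, and Section 14.1 describes ongoing monitoring by AstraZeneca.

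All of this stands and keeps the point small. None of these routes is the DSMC's own decision on suspension.

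A second reply is that Section 10.3.2 asks for all such events without a time limit, and that Appendix 6 sets only a minimum. Appendix 6 indeed does not bar later reporting. But Section 10.3.2 defers to it, so the mandatory part still ends at day 30.

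A third reply concerns noise. Appendix 6 treats any grade 4 event not listed in the protocol as unexpected, and patients may receive adjuvant treatment after surgery. A blanket 90-day rule would pull in toxicities of that treatment. This is correct, and the fix is narrowed for that reason.

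**Conclusion.** The point holds as a low-priority improvement. On the default reading, a durvalumab-related death or unexpected grade 4 event on days 31 to 90 need not receive DSMC suspension review, although the follow-up that would detect it is already planned.

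A reader might infer more, and the documents do not support it:
- **That 30 and 90 days contradict each other.** A notification window may be shorter than a recording window.
- **That late events go unseen or unreported.** They are recorded and reach other bodies.
- **That AstraZeneca would hear of such an event only monthly or quarterly.** Section 10.3.2 has wording to that effect for serious events not needing expedited FDA reporting, but it is in tension with the immediate notification in Section 10.3. No delay can be built on it.
- **That 67% of the risk is unreviewed.** The figure is calendar time. The documents give no event rate for days 31 to 90, so I state no probability; such events should be rare.

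The conclusion assumes that the longer-window clause does not apply. If it does, and AstraZeneca's 90-day requirement governs, only a clarifying sentence is missing. A short part of Appendix 6 was not in the text I had, so the statement that the protocol is silent on this is limited to the rest.

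**What to change.** Add to the DSMC paragraph of Section 10.3.2 that, for this study, DSMC reporting runs through 90 days after the last dose of durvalumab for:
- all grade 5 events not clearly due to disease progression; and
- unexpected grade 4 events for which the investigator answers yes to the causality question in Section 10.2.2.

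Keep the 30-day window of Appendix 6 for all other reportable events, including unplanned hospitalization and grade 4 events attributed to surgery or adjuvant therapy.

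The events are already collected, graded, assessed for causality and entered in WISER, so no new visit, form or committee is needed. The cost is a few extra notifications (the documents do not allow a count), two windows for staff to apply, and the DSMC's agreement to a study-specific departure from its standard procedure.
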